9.4.2.2 Efficacy Analyses

Endpoint	Statistical Analysis Methods
Primary	The primary inferential comparisons of the OS primary endpoint between tarlatamab and SOC arms will be made using a stratified log-rank test controlling for the randomization stratification factors, using the ITT analysis set. The HR and its 95% CI will be estimated using a Cox proportional hazards model stratified by the randomization stratification factors. Stratum that is too small may be collapsed in the stratified log-rank analysis. The distribution of OS, including the median and quartiles and their corresponding 95% CIs will be characterized using the Kaplan-Meier method. The OS rates for selected landmarks (eg, 1 year and 2 years) will be reported with the 95% CI.
Secondary	PFS will be analyzed using the same approach as OS. Further details of the censoring rules will be described in the SAP. The PFS rate at 1 year will be reported with the 95% CI. The descriptive analysis of ORR will use the Cochran-Mantel-Haenszel chi-square test controlling for the randomization stratification factors. An estimate of the common odds ratio (95% CI) will be provided as a measure of the relative treatment effect. ORR will be calculated and the 95% CI will be estimated using the Clopper-Pearson Method.

	
The descriptive analysis of DOR will be provided using the same methods as OS.
 
The change from baseline over time to 18 weeks in symptoms of chest pain and cough as measured by a single question from EORTC-QLQ-LC13 will be analyzed using generalized linear mixed model for repeated measures with cumulative logit link. The change from baseline over time to [redacted] weeks in symptoms of dyspnea as measured by a multiple item dyspnea domain from EORTC-QLQ-C30 and EORTC-QLQ-LC13 Symptom Scores, change from baseline over time to [redacted] weeks in physical functioning and global health status as measured by QLQ-C30 Domain Scores will be analyzed using a mixed model for repeated measurement (MMRM). Missing data for the MMRM will be handled under the assumption of missing at random (MAR).

Exploratory	Will be described in the SAP finalized before database lock

OR = objective response; ORR = objective response rate; PFS = progression free survival; SAP = statistical analysis plan; SOC = standard of care.

9.4.2.3 Safety Analyses

9.4.2.3.1 Adverse Events

Subject incidence of all treatment-emergent adverse events will be tabulated by system organ class and preferred term. Summary tables of the subject incidence of treatment-emergent adverse events, and grade ≥ 3 , serious, treatment-related, and fatal treatment-emergent adverse events.

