Chemotherapy-free interval is defined as the number of days elapsed between the last dose of prior chemotherapy and the date of first suspicion of disease relapse or progression (clinical or radiological). For example, if a patient experiences seizure and a brain metastasis progression is detected 48-hours after the seizure occurred, the date of progression is the date of this first seizure episode. Additionally, global enrollment will be monitored in order to ensure the majority of subjects have prior anti-PD-(L)1 exposure. **For patients with no exposure to prior anti-PD-(L)1, the reason for nonuse will be collected.**

Subjects will receive study treatment until investigator-determined radiographic disease progression per RECIST 1.1, unacceptable toxicity, withdrawal of consent, death, or end of study as determined by the sponsor (whichever occurs first). Following documented radiographic progression, the subject may remain on study treatment provided certain criteria are met. Refer to Section [6.1.7](#) for more details.

Upon permanent discontinuation from study treatment for any reason, an SFU visit will be performed approximately **60** (+ 5) days after last dose of study treatment, regardless of subsequent anti-cancer therapy that has been initiated within that period.

After the SFU visit, subjects will be followed in LTFU for survival every 12 weeks (\pm 14 days) from the SFU visit (or last imaging visit, whichever is later) for up to 3 years

after the last subject is enrolled, or 1 year from the subject's last dose of study treatment, whichever is later. **Ad hoc vital status (survival status) collection may be required to support key study analysis.**

The median time of subject's participation in the study treatment period will be approximately 4 to 6 months with median study duration to be approximately 9 to 12 months. The total study duration is expected to be approximately 4 years from the first subject enrolled to the final analysis.

Number of Subjects

Approximately █ subjects will be enrolled at approximately 240 sites globally.

Summary of Subject Eligibility Criteria

Male and female subjects (age \geq 18 years [or legal adult age within country, whichever is older]) with histologically or cytologically confirmed relapsed SCLC who progressed following 1 platinum-based regimen.

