
 Compare the efficacy of tarlatamab with SOC as assessed by PFS at 1 year from randomization, objective response (OR), disease control (DC), and duration of response (DOR) based on investigator assessment per RECIST 1.1, and OS at 1 year, 2 years, and 3 years from randomization 	
 OR, defined as best overall response (BOR) of complete response (CR) + partial response (PR) DC, defined as CR + PR + stable disease (SD) DOR, defined as the time from the first documentation of OR until the first documentation of disease progression or death due to any cause, whichever occurs first. Only subjects who have achieved OR will be evaluated for DOR PFS rate at 1 year from randomization

	
 OS rate at 1 year, 2 years, and 3 years from randomization

 Compare the safety and tolerability of tarlatamab with SOC 	
 Incidence of treatment-emergent adverse events including grade ≥ 3 treatment-emergent adverse events, serious treatment-emergent adverse events, treatment-emergent adverse events leading to treatment discontinuation, fatal treatment-emergent adverse events, and treatment-related adverse events

 Characterize the pharmacokinetics (PK) of tarlatamab 	
 Serum concentrations of tarlatamab

 Evaluate the immunogenicity of tarlatamab 	
 Incidence of anti-tarlatamab antibody formation

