4.1 Overall Design

This is an open-label, randomized, multi-center, phase 3 study that will evaluate efficacy and safety of tarlatamab (AMG 757) compared with SOC therapy for the treatment of subjects with SCLC who have progressed after 1 prior line of platinum-containing therapy.

The study consists of a 21-day screening period, a treatment period, an SFU visit, and an LTFU period.

Subjects will be randomized with a 1:1 allocation ratio to receive tarlatamab or SOC therapy (lurbinectedin or topotecan in US, Canada, Australia, Singapore, Korea; amrubicin in Japan; topotecan in all countries except Japan).

Randomization will be stratified by:

- Prior anti-PD-1 or prior anti-PD-(L)1 exposure (yes vs no)
- Chemotherapy-free interval (\geq 180 days; < 180 to \geq 90 days; < 90 days)
- Presence (previous or current) of brain metastases (yes or no)
- Standard of care (topotecan/amrubicin vs lurbinectedin)

Chemotherapy-free interval is defined as the number of days elapsed between the last dose of prior chemotherapy and the date of first suspicion of disease relapse or progression (clinical or radiological). For example, if a patient experiences seizure and a brain metastasis progression is detected 48-hours after the seizure occurred, the date of progression is the date of this first seizure episode. Additionally, global enrollment will be monitored in order to ensure the majority of subjects have prior anti-PD-(L)1 exposure. **For patients with no exposure to prior anti-PD-(L)1, the reason for nonuse will be collected.**

Study treatment will be administered as follows:

- Tarlatamab will be administered as a 60-minute intravenous (IV) infusion with a step dose (1 mg tarlatamab) on cycle 1 day 1 (C1D1) followed by 10 mg target dose on C1D8 and C1D15, and Q2W thereafter (ie, C2+ D1/D15 dosing) in a 28-day cycle.
 - Monitoring - cycle 1: Monitoring required for 6 to 8 hours post-infusion at C1D1 and C1D8.
 - Cohabitant (caregiver) support for 24 hours post-infusion and the ability to stay within 1 hour of a hospital for 24 hours is required.
 - Counseling the subject and caregiver on signs and symptoms of CRS and ICANS by a health care provider is required prior to discharge.

- Subjects return to site on cycle 1 day 2 and cycle 1 day 9 for vital signs and physical examination.
 - At subsequent visits, additional monitoring may be required post-infusion. Refer to Section [6.1.1 \(Table 6-1\)](#).
- Pre- and post-infusion medication requirements:

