 - Dexamethasone: 8 mg IV (or equivalent) will be administered within 1 hour prior to tarlatamab infusion on C1D1 and C1D8
 - IV hydration: 1 L normal saline over 2 to 4 hours following tarlatamab doses on C1D1 and C1D8
- Standard of care (21-day cycle): Standard of care will be administered as follows in a 21-day cycle:
 - Lurbinectedin (US, Canada, Australia, Singapore, and Korea) will be administered as 3.2 mg/m² IV on day 1 every 3 weeks
 - Topotecan (all countries, except Japan and China) will be administered as IV at 1.5 mg/m² or oral at 2.3 mg/m²/day on days 1, 2, 3, 4, and 5 every 3 weeks
 - Topotecan (China mainland [China mainland in this clinical study shall be referred to as "China"]]) will be administered as IV at 1.2 mg/m² or other locally approved dose or oral at 2.3 mg/m²/day on days 1, 2, 3, 4, and 5 every 3 weeks
 - Amrubicin (Japan) will be administered as 40 mg/m² IV on days 1 to 3 every 3 weeks

Subjects will receive study treatment until investigator-determined radiographic disease progression per RECIST 1.1, unacceptable toxicity, withdrawal of consent, death, or end of study as determined by the sponsor (whichever occurs first). Following documented radiographic progression, the subject may remain on study treatment provided criteria are met. Refer to Section [6.1.7](#) for more details.

Upon permanent discontinuation from study treatment for any reason, an SFU visit will be performed approximately **60** (+5) days after last dose of study treatment, even if subsequent anti-cancer therapy has been initiated within that period.

After the SFU visit, subjects will be followed in LTFU for survival every 12 weeks (\pm 14 days) from the SFU visit (or last imaging visit, whichever is later) for up to 3 years after the last subject is enrolled, or 1 year from the subject's last dose of study treatment, whichever is later. **Ad hoc vital status (survival status) collection may be required to support key study analysis.**

Approximately [REDACTED] subjects will be enrolled at approximately 240 sites globally. The median time of subject's participation in the study treatment period will be approximately 4 to 6 months with median study duration to be approximately 9 to 12 months. The total study duration is expected to be approximately 4 years from the first subject enrolled to

the final analysis. Participants in this clinical investigation shall be referred to as “subjects”. For the sample size justification, see Section 9.2.

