8.4.6 Adverse Events and Serious Adverse Events

The method of recording, evaluating, and assessing causality of adverse events, and serious adverse events and the procedures for completing and transmitting serious adverse event reports are provided in [Section 11.4 with the following exceptions:](#)

CRS and ICANS will be graded according to American Society for Transplantation and Cellular Therapy (Lee et al, 2019) as described in [Table 6-2](#) and [Section 11.11](#).

8.4.6.1 Time Period and Frequency for Collecting and Reporting Safety Event Information**8.4.6.1.1 Adverse Events**

The adverse event grading scale to be used for this study will be the CTCAE v5.0 and is described in Section 11.4.

The investigator is responsible for ensuring that all adverse events observed by the investigator or reported by the subject that occur after the first dose of investigational product(s) or noninvestigational product(s)/auxiliary medicinal product(s) through the SFU visit or **60** days after the last dose of investigational product(s) or non-investigational product(s)/auxiliary medicinal product(s), whichever is later, are reported using the Events CRF.

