9.3 Populations for Analysis

The following populations are defined:

Population	Description
ITT analysis set	All randomized subjects. All subjects will be analyzed according to the randomized treatment arm. The ITT analysis set will be used for primary and secondary efficacy endpoints, unless specified otherwise.
Safety analysis set	All subjects who take at least 1 dose of study treatment. Subjects will be analyzed according to the study treatment they actually received.

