**Exposure-Adjusted Event Rate of TEAE**

Exposure-adjusted event rate will be calculated as:

$$(\text{Total number of TEAEs}) / (\text{total participant years of exposure of tarlatamab}) * 100$$

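### The tarlatamab versus SOC adverse event comparison rests on crude subject incidence in the protocol and the supplied iSAP, so unequal time on treatment could pass for a difference in toxicity; add first-event exposure-adjusted rates for both arms

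*Protocol*

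**What the plan says.** - **Objective.** Protocol Section 3 has the secondary objective "Compare the safety and tolerability of tarlatamab with SOC". The endpoint is the incidence of treatment-emergent adverse events (TEAEs), with grade 3 or higher, serious, fatal and treatment-related events and events leading to discontinuation named as categories.
- **Planned summary.** Protocol Section 9.4.2.3.1 states "Subject incidence of all treatment-emergent adverse events will be tabulated by system organ class and preferred term". It adds incidence tables for grade 3 or higher, serious, treatment-related and fatal TEAEs, but does not list TEAEs leading to discontinuation. It gives no person-time denominator, time-to-first-event summary or between-arm interval.
- **Population.** The safety analysis set is "All subjects who take at least 1 dose of study treatment", analysed as treated (Section 9.3).
- **Window.** Section 8.4.6.1.1 collects adverse events from first dose to the safety follow-up visit or 60 days after last dose, whichever is later.
- **Time on treatment.** "Subjects will receive study treatment until investigator-determined radiographic disease progression per RECIST 1.1", or until toxicity, withdrawal, death or study end (Section 4.1). Section 6.1.7 lets subjects in either arm continue past progression under conditions. The one expected duration is study-wide: "The median time of subject's participation in the study treatment period will be approximately 4 to 6 months".
- **Exposure.** Sections 9.4.2.3.7 and 9.4.2.3.8 summarise exposure separately from adverse events.
- **iSAP.** Its Section 3 defines an exposure-adjusted event rate as all TEAEs divided by "total participant years of exposure of tarlatamab", times 100, and Section 5.4.4.1 applies it to several TEAE categories. By scope (Sections 1 and 5.3.1) it covers tarlatamab recipients only.

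**The concern.** A crude proportion depends on both the hazard of an event and the time during which the event can be counted. Here the second factor depends on treatment. The trial tests whether tarlatamab prolongs PFS. If it does, and treatment generally runs to progression, the tarlatamab arm can be expected to stay on drug longer and to be observed longer for adverse events.

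The longer-treated arm would then show a higher incidence even if the monthly risk were the same in both arms. The same mechanism could mask a genuine tolerability advantage of the longer-treated arm. The categories most exposed are those whose risk persists through treatment. Some serious, grade 3 or higher and discontinuation events may be of this kind, and the endpoint names all three categories.

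**Working it through.** The documents give no adverse event rate by arm and no duration by arm, so there is no figure of the plan to reproduce. The check asks how large a difference unequal exposure alone could create.

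**Inputs**
- From the documents: a 60-day window after last dose, w = 60/30.44 = 1.97 months; one study-wide median of 4 to 6 months on treatment.
- Assumed: arm medians of 4/5, 4/6, 3/6 and 2/6 months; the same constant monthly hazard L in both arms, scanned over its whole range; no allowance for death cutting the window short.

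**Formulas** for incidence with median treatment time m
- Fixed time: 1 − exp(−L(m + w)).
- Exponential time, with μ = ln 2/m: 1 − exp(−Lw) · μ/(μ + L).

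**Worked cases at the hazard giving the largest difference**
- 3 vs 6 months, exponential, L = 0.106: 44.4% vs 57.7%, 13.3 points.
- 3 vs 6 months, fixed, L = ln(7.97/4.97)/3 = 0.157: 54.3% vs 71.5%, 17.2 points.
- 4 vs 6 months, exponential, L = 0.096: 46.7% vs 54.8%, 8.1 points.
- 4 vs 6 months, fixed, L = ln(7.97/5.97)/2 = 0.144: 57.8% vs 68.4%, 10.6 points.

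| Medians (months) | Largest difference, exponential / fixed | Short-arm incidence at which it reaches 10 points |
|---|---|---|
| 4 vs 5 | 4.4 / 5.7 | never |
| 4 vs 6 | 8.1 / 10.6 | never / about 45–70% |
| 3 vs 6 | 13.3 / 17.2 | about 21–71% / 20–86% |
| 2 vs 6 | 19.9 / 25.1 | about 11–81% / 11–89% |

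**Rare and near-universal events.** At 3 vs 6 months, an event with 10% short-arm incidence differs by 5.8 / 5.5 points, and one with 90% by 4.1 / 7.5 points.

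**Early events** (exponential time, hazard confined to the first c months, largest difference)
- c = 1 or 2: 0 points, because the 60-day window covers that period in both arms.
- c = 3: at most 1.5 points, even at 2 vs 6 months.
- c = 6: at most 2.7 (4 vs 6), 5.0 (3 vs 6) and 8.9 (2 vs 6) points.

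**Does the proposed rate remove the artefact?** Under a constant hazard, expected time at risk to first event or end of window equals incidence divided by L, so the first-event rate returns L whatever the window. With L = 0.15 and 3 vs 6 months, crude incidence by the exponential formula is 54.9% vs 67.6%. A simulation of 2,000,000 subjects per arm gave rates of 15.0 vs 15.0 per 100 person-months (15.0 × 12 = 180 per 100 subject-years).

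**The case against.** **The study SAP may already cover this.** Protocol Section 9.4 calls itself a summary, and Section 11.4 leaves the TEAE definition to the SAP. The supplied document is an integrated safety plan that refers derivations to the individual study SAPs. A reader might infer that no exposure-adjusted SOC rate will exist. The documents do not support that: SOC is absent from the iSAP because of its scope, and the study SAP has not been seen. This stands, and limits the point to the protocol and the iSAP. The TEAE window itself may also be set in the study SAP; what is documented is the collection window.

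**Crude incidence is the stated endpoint.** Safety is descriptive, and exposure is tabulated, so a reader can see an imbalance. This also stands: the plan analyses what it defines. But separate exposure tables do not let a reader work out how much of an incidence difference is due to time at risk.

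**Ten points is not a general result.** A reader might infer that unequal exposure will by itself create differences of 10 points or more. That generally needs about a two-fold difference in duration and a persisting risk of intermediate incidence. Placing the two ends of the stated 4 to 6 month range in opposite arms reaches 10 points only with fixed times. This stands.

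**The commonest tarlatamab event is early.** Protocol Section 4.4 places CRS mostly after the first two infusions. There the artefact is about zero, and an exposure-adjusted rate would itself mislead, because later low-risk time dilutes it. This stands, and is why the crude tables should stay.

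**Conclusion.** The concern holds in a limited form. In the protocol and the supplied iSAP, the only adverse event summary that compares tarlatamab with SOC is crude subject incidence, over a collection period that lengthens with treatment. If tarlatamab delays progression, that comparison mixes toxicity with length of observation for events whose risk persists.

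The size is conditional: up to about 13 to 17 points at 3 versus 6 months and about 8 to 11 points at 4 versus 6 months, less for rare or near-universal events, and about zero for events confined to the first one or two months. These figures rest on equal constant hazards and on arm-specific durations that the documents do not give. They show what could happen and do not predict the trial's result.

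This is an inexpensive improvement that should be made. It does not show that the planned tables are wrong, or that the sponsor lacks an adjusted comparison elsewhere.

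**What to change.** In protocol Section 9.4.2.3.1, keep the crude tables. Add, for both arms and for every TEAE category in the secondary endpoint, including TEAEs leading to discontinuation, the first-event exposure-adjusted incidence rate: subjects with a first event per 100 subject-years at risk, counting time from first dose to the first event or the end of the window that includes the 60 days after last dose. Give the rate difference with a 95% CI. If the study SAP already specifies this, a cross-reference is enough.

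Specify the first-event rate explicitly. The iSAP rate counts all events, so repeat events in one subject raise it; it should not simply be extended to SOC.

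The cost is a few table columns from data already collected. The downside is that the rate assumes a roughly constant hazard. State beside the tables that early events such as CRS should be read from crude incidence; a cumulative incidence curve by arm is an option where the hazard clearly changes over time.

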9.4.2.3.2 Laboratory Test Results

The analyses of safety laboratory endpoints will include summary statistics over time. Shifts in grades of safety laboratory values between the baseline and the worst on-study value will be tabulated.

9.4.2.3.3 Vital Signs

The analyses of vital signs will include summary statistics over time. The incidence and percentage of abnormal changes in vital signs will be tabulated.

9.4.2.3.4 Physical Measurements

The analyses of physical measurements will include summary statistics at baseline.

9.4.2.3.5 Electrocardiogram

The ECG measurements from this clinical study were performed as per SOC for routine safety monitoring, rather than for purposes of assessment of potential QTc effect. Since these evaluations may not necessarily be performed under the rigorous conditions expected to lead to meaningful evaluation of QTc data; summaries and statistical analyses of single ECG measurements are not planned, and these data would not be expected to be useful for meta-analysis with data from other trials.

9.4.2.3.6 Antibody Formation

The incidence and percentage of subjects who develop anti-tarlatamab antibodies at any time will be tabulated.

9.4.2.3.7 Exposure to Investigational Product

The number of cycles, duration, the cumulative dose, and the average dose of investigational product administered will be summarized.

9.4.2.3.8 Exposure to Non-investigational Product(s)/Auxiliary Medicinal Product(s)

Descriptive statistics will be produced to describe the exposure to noninvestigational product(s)/auxiliary medicinal product(s).

9.4.2.3.9 Exposure to Concomitant Medication

Number and proportion of subjects receiving therapies of interest will be summarized by preferred term for each treatment group as coded by the World Health Organization Drug dictionary.

11.1 Appendix 1. List of Abbreviations

Abbreviation	Explanation
ALP	alkaline phosphatase
ALT	alanine aminotransferase
ASR	Annual Safety Report
AST	aspartate aminotransferase
BCRP	breast cancer resistance protein
BIL	Bilirubin
BiTE	Bispecific T cell Engager
BOR	best overall response
BPI-SF	Brief Pain Inventory - Short Form
BSA	body surface area
CARTOX	CAR-T-cell-therapy-associated TOXicity
CAV	cyclophosphamide, adriamycin, and vincristine
CFI	Chemotherapy-free interval
CFR	US Code of Federal Regulations
CNS	central nervous system
COVID-19	coronavirus disease 2019
CR	complete response
CRF	case report form
CRO	contract research organization
CRS	cytokine release syndrome
CT	computed tomography
CTCAE	Common Terminology Criteria for Adverse Events
[REDACTED]	[REDACTED]
CYP3A	cytochrome P450 3A
DCR	disease control rate
DILI	drug-induced liver injury
DLL3	delta-like ligand 3
DMC	data monitoring committee
DOR	duration of response
DSUR	Development Safety Update Report
ECG	Electrocardiogram
ECHO	Echocardiogram
ECOG	Eastern Cooperative Oncology Group
eCRF	electronic case report form

eGFR	estimated glomerular filtration rate
EDC	electronic data capture
EGFR	epidermal growth factor receptor
EOI	end of infusion
EORTC QLQ-C30	European Organization for Research and Treatment of Cancer Quality of Life Questionnaire 30
EORTC-QLQ-LC13	European Organization for Research and Treatment of Cancer Quality of Life Questionnaire Lung Cancer 13
EOT	end of treatment
EP	platinum-etoposide
EQ5D-5L	5-level EuroQol 5-dimension
ES	extensive stage
EU	European Union
FACT-G	Functional Assessment of Cancer Therapy – General
FDA	US Food and Drug Administration
FDG	Fluorodeoxyglucose
FFPE	formalin-fixed, paraffin-embedded
FIH	first-in-human
FNA	fine needle aspiration
FSH	follicle-stimulating hormone
GCP	Good Clinical Practice
G-CSF	granulocyte colony-stimulating factor
HBV	hepatitis B-virus
HBsAg	hepatitis B surface antigen
HCV Ab	hepatitis C antibody
HIPAA	Health Insurance Portability and Accountability Act
HIV	human immunodeficiency virus
HLE	half-life extended
HR	hazard ratio
IBG	independent biostatistics group
ICANS	immune effector cell-associated neurotoxicity syndrome
ICE	immune effector cell-associated encephalopathy
ICF	informed consent form
ICH	International Council for Harmonisation
ICP	intracranial pressure
IEAS	interim efficacy analysis set
IEC	independent ethics committee
Ig	Immunoglobulin

IHC	Immunohistochemistry
INN	International Nonproprietary Name
INR	international normalized ratio
IRB	institutional review board
IRT	interactive response technology
IV	Intravenous
LDH	lactate dehydrogenase
LS	limited stage
LTFU	long-term follow-up
LVEF	left ventricular ejection fraction
MedDRA	Medical Dictionary for Regulatory Activities
MAR	missing at random
MMRM	mixed model for repeated measurement
mOS	median overall survival
MRI	magnetic resonance imaging
MUGA	multigated acquisition
N/A	Not applicable
NA	nuclear antigen
NCT	National Clinical Trial
NE	not evaluable
NSCLC	non-small cell lung cancer
NYHA	New York Heart Association
OR	objective response
ORR	objective response rate
OS	overall survival
OSF	other safety findings
PCR	polymerase chain reaction
PD	progressive disease
PD-1	programmed cell death 1
PD-(L)1	programmed cell death ligand 1
PET	positron emission tomography
PFS	progression-free survival
PGIC	Patient Global Impression of Change
PGIS	Patient Global Impression of Severity
P-gp	P-glycoprotein
PK	Pharmacokinetic
PR	partial response
PRO	patient-reported outcome

PS	performance status
PT	prothrombin time
PTT	partial thromboplastin time
Q2W	every 2 weeks
QTc	corrected QT interval
QTL	quality tolerance limit
RECIST 1.1	Response Evaluation Criteria in Solid Tumors Version 1.1
SAP	statistical analysis plan
SARS-CoV-2	severe acute respiratory syndrome coronavirus 2
scFc	single chain fragment crystallizable
SCLC	small cell lung cancer
SCR	Screening
SD	stable disease
SFU	safety follow-up
SOC	standard of care
SS	special situations
TBL	total bilirubin
TLS	Tumor lysis syndrome
ULN	upper limit of normal
US	United States
USP	United States Pharmacopeia
UTI	urinary tract infection
VAS	visual analogue scale

